6.5 SECONDARY ANALYSES

6.5.1 Efficacy

All parameters listed below will be examined descriptively in a first step and only analyzed using exploratory statistical methods if notable differences or discrepancies are observed. The aim of exploratory data analysis is to generate hypotheses as a basis for future research projects.

Secondary endpoints related to alcohol self-administration will include:

a. Difference between visit 2 and visit 5 of the "break points" in the "progressive work" scheme for working for alcohol. The "break point" represents the performance threshold at which participants decide it is no longer worth working for another reward (alcohol) and thus stop the CAT before reaching the next reward.

The comparison of the difference in break points between Visit 2 and Visit 5 among the three groups will be conducted descriptively using frequency tables, median, range, maximum, minimum, and appropriate graphical representation.

b. Difference in maximum and mean blood alcohol concentration (BAC) achieved during alcohol self-administration between visits 2 and 5.

This parameter will be analyzed using analyses of variance (ANOVAs).

c. Difference in the cumulative number of work trials for saline solution in the "constant attention task" between visit 2 and visit 5:"

The differences in the three groups will be compared using ANOVA.

d. Investigation of the primary and the above-mentioned secondary parameters of alcohol self-administration, considering only the first and second halves of the experiment. For this purpose, the cumulative number of work trials for alcohol and saline in the CAT will be recorded every 30 seconds during an experiment.

The analyses will be conducted according to the primary and the relevant secondary parameters of alcohol self-administration.

In addition, the following secondary questions will be investigated:

1. does the administration of acamprosate or calcium ions compared to placebo lead to altered subjective perception of alcohol effects?

The subjective perception of alcohol effects will be measured using visual analog scales ("quizzer") before, during and after the experiment at visits 2 and 5 in order to compare their alcohol-induced changes between the 3 treatment arms. The values and the "slopes" (changes) between two measurement points will be analyzed.

Repeated measures ANOVA will be used for analysis, with primary and secondary endpoints of alcohol infusion as covariates. The relationship between alcohol infusion endpoints and subjective data will be further examined using correlation analyse.

2. can the efficacy of acamprosate or calcium ions be predicted by basal levels or changes over time in measures of body calcium reserves indicating possible calcium deficiency?

The blood levels of total calcium, phosphate, magnesium, albumin, parathyroid hormone, 25-hydroxyvitamin D will be measured at visit 2 and visit 5. Baseline values and the difference in values between V2 and V5 will be examined for their relation to the primary endpoint in the three treatment arms.

The relationship between body calcium reserves and efficacy will be investigated using correlation analyses and regression analyses. Group comparisons will be conducted using ANOVA.

3. does the administration of acamprosate or calcium ions reduce alcohol cravings in daily life?

Alcohol craving in daily life will be measured using the "Obsessive Compulsive Drinking Scale" (OCDS) before both self-administration experiments to compare treatment-related changes between the 3 treatment arms.

The change in the total OCDS score and the two subscores will be compared between the three groups using repeated measures ANOVAs.

4. does the frequency of reported alcohol consumption during the imposed abstinence period differ between treatment groups, and how does this affect the work for alcohol after the imposed abstinence period?

Violations of the imposed abstinence will be recorded as the percentage (%) of days with alcohol consumption reported (by TLFB) to compare them between the three treatment arms and to examine their influence on the primary outcome measure.

Group comparisons regarding the frequency of alcohol consumption will be performed using ANOVA. The influence on the primary endpoint will be examined using regression analysis and correlation analysis.

5. does participation in the study promote the motivation to change drinking habits or alter drinking habits or the utilization of addiction treatment services?

Motivation to change drinking habits:

The "Readiness to change" questionnaire will be used to determine which of the three "stages of change" in drinking habits the participants are currently in. Differences in "stages of change" will be assessed at three time points: before study participation (screening), after completion of the study procedures (visit 6) and after completion of the brief intervention (telephone follow-up). These assessments will be considered independently of the treatment arm. The numbers of participants who increase, maintain, or decrease in their stage of change will be recorded.

The stages of change will be analyzed using the Wilcoxon sign-rank test (scaled ordinally). Changes in the stage of change will be analyzed using ordinal logistic regression.

Drinking habits:

Drinking habits will be assessed using the timeline follow-back interview (TLFB) at screening (or re-screening), at visits 1, 3 and 6 and at the telephone follow-up. Changes in drinking habits due to study participation will be recorded by comparing drinking amounts during the 45 days before the study (measured at the screening or re-screening) with those after the end of the study (telephone follow-up interview). The following points are examined in each of the 3 treatment arms:

- a. percentage of drinking days,
- b. average amount of alcohol consumed per drinking day,
- c. percentage of days with heavy alcohol consumption (over 60 g for men and 48 g for women = "binge days"), and
- d. average amount of alcohol consumed on these binge days

Comparisons over time regarding these parameters will be conducted using repeated measures ANOVA.

Utilization of addiction treatment services:

The use of addiction treatment services will be recorded by determining whether the participants have ever accessed any addiction treatment services (e.g. addiction-specific counseling/treatment by an addiction counseling center, general practitioner, psychologist, psychiatrist or hospital) in comparison before study participation (at screening) and afterwards (visit 6 and telephone follow-up survey)

Changes in behavior regarding the use of addiction treatment services will be categorized and analyzed using chi-square tests.

6. is the activity of secreted sphingomyelinase a suitable biomarker for alcohol consumption and prediction of medication effects?

For this purpose, the baseline values and the changes in the activity of secreted acid sphingomyelinase will be measured at screening and both self-administration experiments (V2 and V5) in serum. These will be examined in relation to drinking behavior (TLFB values), primary and secondary endpoints of alcohol self-administration and medication effects.

Analysis will be conducted using correlation analyses.

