2 ANALYSIS POPULATIONS

2.1 DEFINITIONS

The intent-to-treat population (ITT) to be analyzed comprises all randomized subjects who were administered the investigational product (excluding the placebo lead-in medication and alcohol) at least once. The statistical analysis of this population determines whether the results are statistically significant or statistically non-significant.

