4.3 SECONDARY ENDPOINTS

4.3.1 Endpoints related to efficacy

- 1. Additional parameters of alcohol self-administration:
 - Difference between visit 2 and visit 5 of the "break points" [BPALC] in the "progressive work" task for alcohol. The "break point" corresponds to the performance requirement at which subjects decide it is no longer worth working for another reward (alcohol) and thus stop working on the CAT before reaching the next reward.
 - Difference in maximum blood alcohol concentration (BAC) [BACMAX] and b) mean BAC [BACMEAN] during alcohol self-administration between visits 2 and 5
 - Difference between visit 2 and 5 in the cumulative number of work cycles for saline [CATWAT] in the "constant attention task"
 - Analysis of the primary and the above-mentioned secondary parameters of alcohol self-administration with separate consideration of only the first and second half of the experiment respectively. For this purpose, the cumulative number of work cycles for alcohol and saline in the CAT is recorded every 30 seconds during an experiment [CATALC_T0 to CATALC_T300].
- 2. The subjective alcohol effects will be measured using visual analog scales ("quizzer") before, during and after the experiment at visits 2 and 5 in order to

compare alcohol-induced changes between the 3 treatment arms. The raw values and the "slopes" (increases) between consecutive measurement points will be used for analysis.

The following measures will be collected at 4 points in time (before the experiment, twice during the experiment, once after the experiment):

- a) stimulation [VAS1T1, VAS1T2, VAS1T3, VAS1T4],
- b) Sedation [VAS2T1, VAS2T2, VAS2T3, VAS2T4]
- c) Negative Feelings [VAS3T1, VAS3T2, VAS3T3, VAS3T4]
- d) Desire for more alcohol [VAS4T1; VAS4T2; VAS4T3; VAS4T4]
- e) Positive feelings [VAS5T1; VAS5T2; VAS5T3; VAS5T4]
- f) Drinks [VAS6T1; VAS6T2; VAS6T3; VAS6T4]
- g) Feeling drunk [VAS7T1, VAS7T2; VAS7T3; VAS7T4]
- h) Thirsty [VAS8T1; VAS8T2; VAS8T3; VAS8T4]
- 3. Parameters of body calcium reserves will be measured: The blood levels of total calcium [CAL], phosphate [PHOS], magnesium [MG], albumin [ALB], parathyroid hormone [PAHO], 25-hydroxyvitamin D [VITD] at visit 2 and visit 5. Baseline values and the difference in values between V2 and V5 will be considered to examine their relationship to the primary endpoint value in the three treatment arms.

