5 MISSING VALUES AND OUTLIERS

5.1 MISSING VALUES

If missing values occur for the primary endpoint (e.g. due to protocol regulations or withdrawal of consent), these will be replaced after reviewing the data using suitable methods.

Additionally, sensitivity analyses will be conducted, including a complete-case analysis (where only participants with all data required for calculating the primary endpoint are analyzed) and, if necessary, data imputation using suitable methods.

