7 SOFTWARE

The statistical analyses will be performed using the SPSS software and SAS System for Windows.

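### Repeated measures ANOVA for the subjective-effect scales, as standardly run, drops participants with any missing rating in the model, and Section 5.1 has no missing-data rule for these scales

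*SAP*

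**What the plan says.** SAP Section 4.3.1, item 2, lists eight visual analog scales, rated "before, during and after the experiment at visits 2 and 5". On timing within a session it states: "The following measures will be collected at 4 points in time (before the experiment, twice during the experiment, once after the experiment". The purpose is to compare alcohol-induced changes across the three arms. Both the raw values and the slopes "between consecutive measurement points will be used for analysis".

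Section 6.5.1, question 1, names the method: "Repeated measures ANOVA will be used for analysis, with primary and secondary endpoints of alcohol infusion as covariates". It does not say whether V2 and V5 enter one model or separate models. Section 6.5.1 also makes all its secondary analyses descriptive first, with exploratory testing only where something notable appears.

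Section 5.1 opens with "If missing values occur for the primary endpoint". Its complete-case sensitivity analysis is also tied to that endpoint: "only participants with all data required for calculating the primary endpoint are analyzed". The imputation mentioned at the end of the section belongs to the same set of sensitivity analyses.

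Section 2.1 defines the ITT set as "all randomized subjects who were administered the investigational product" at least once. Attendance at V5 is a condition of the per-protocol set only (Section 2.2).

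Section 7 states: "The statistical analyses will be performed using the SPSS software and SAS System for Windows". No procedure is named.

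**The concern.** Repeated measures ANOVA in its standard form needs a value in every within-participant cell of the model. One missing rating removes the participant for that scale, together with all the ratings that were given. Because exclusion works scale by scale, the eight scales can end up analysed on different subsets.

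The method also assumes sphericity over the four time points, and the SAP mentions neither a check nor a correction.

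No rule in the SAP softens this. Section 5.1 itself expects missing primary-endpoint values, for instance after withdrawal of consent. A participant who withdraws before V5 lacks four of the eight ratings on every scale but stays in the ITT set. What is at stake is precision in the first secondary objective, and possibly selection if completeness is related to what is being rated.

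**Working it through.** The SAP gives no missing rate, sample size or power for this analysis, so there is no figure of its own to reproduce. The loss can be shown only as a range under assumptions.

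**Inputs**
- Ratings per scale and session: 4 (Section 4.3.1).
- Sessions: 2, V2 and V5 (Section 4.3.1), so 4 × 2 = 8 ratings per scale.
- Share of ratings missing, *m*: not in the SAP; assumed 1%, 3% and 5%.
- Model layout: not in the SAP; taken as one visit (4 ratings) or both visits jointly (8 ratings).

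**Formulas for the share of participants lost on one scale**
- Ratings missing independently, one visit: 1 − (1 − *m*)^4.
- Ratings missing independently, both visits jointly: 1 − (1 − *m*)^8.
- Missing ratings consist only of whole V5 sessions: a share *d* of participants lacks 4 of 8 ratings, so *m* = *d* × 4/8 and *d* = 2*m*. The loss is *d*, in a joint model or in a model of V5 alone.

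**Results**

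| Ratings missing (assumed) | Whole V5 sessions | Independent, 4 ratings | Independent, 8 ratings |
|---|---|---|---|
| 1% | 2% | 3.9% | 7.7% |
| 3% | 6% | 11.5% | 21.6% |
| 5% | 10% | 18.5% | 33.7% |

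The 5% row in full: 2 × 0.05 = 0.10; 1 − 0.95^4 = 1 − 0.8145 = 0.1855; 1 − 0.95^8 = 1 − 0.6634 = 0.3366.

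A mixed pattern lies in between. If 10% of participants miss V5 and 1% of the other participants' ratings are missing independently, the share complete on eight ratings is 0.90 × 0.9227 = 0.830, a loss of 17.0%.

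**Slopes.** Four ratings give three slopes per session, and each needs both neighbouring ratings. An ANOVA on all three slopes therefore needs all four ratings, so using slopes does not avoid the loss.

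**Behaviour of the two methods.** Data were simulated for 20 participants with 8 ratings each (160 in total) and one rating was deleted. A repeated measures ANOVA routine (not one from the packages in Section 7) refused the data as unbalanced, so the participant would have to be dropped or the rating imputed. A mixed model used 159 ratings from all 20 participants. Its fit gave convergence warnings because the simulated data had no between-participant variance; this does not affect the count of data retained.

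**The case against.** Much can be said in the plan's favour.

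- **Low stakes.** The analysis is hypothesis-generating and run only if the descriptive step suggests it. That step can use every available rating, and H1 and H2 do not depend on it. This stands, and it limits the weight of the point.
- **Layout not fixed.** A reader might infer that the plan requires all eight ratings. A joint model is the natural reading, because changes at both visits are compared between arms, but the SAP does not write it down. Section 7 names packages and no procedure. The 34% figure is therefore one scenario and not the expected loss.
- **Independence is a strong assumption.** Ratings within a session are likely to go missing together, and clustering reduces the number of participants lost. The whole-session column shows this.
- **Bias through the rated effects.** A reader might infer that sedation or negative feelings end sessions early and so remove late ratings. Nothing in the SAP says so. The fourth rating is taken after the experiment, so an early stop does not by itself remove it. Selection is possible but not shown.
- **Sphericity has a cheaper remedy.** A degrees-of-freedom correction would deal with it, but it would not recover excluded participants.
- **Same method elsewhere.** Craving scores and drinking habits are also analysed by repeated measures ANOVA without a missing-data rule. Those analyses compare two occasions, so sphericity does not arise and fewer values are needed per participant. The gap is widest for the visual analog scales.

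None of this supplies a missing-data rule for these scales or a reason to prefer a complete-case method.

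**Conclusion.** The point holds as an avoidable weakness in a secondary, exploratory analysis. The named method discards partial records in its standard form and assumes sphericity over four time points. The missing-data section does not reach these scales, and the ITT set includes participants who may have no V5 ratings.

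The consequence is lost precision and possible selection in the comparison of subjective effects. At an assumed 5% of ratings missing, the loss is between about 10% and about 34% of participants per scale, depending on the pattern of missingness and the model layout. At an assumed 1% it is about 2% to 8%. These figures rest on assumed rates, and the higher ones on independence across ratings.

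The SAP does not support the claims that the confirmatory tests are affected, that eight complete ratings are an explicit requirement, or that bias is established.

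**What to change.** In Section 6.5.1, question 1, replace repeated measures ANOVA with a linear mixed model per scale, fitted by REML to all available ratings.

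- **Fixed effects:** arm, visit, time point and all their interactions.
- **Covariance:** unstructured within participant. With eight ratings this has 8 × 9/2 = 36 parameters, so name a fallback in case it does not converge, for example heterogeneous autoregressive within visit plus a participant random effect. A random intercept alone should not be the fallback. It imposes compound symmetry, which is itself a form of the sphericity assumption.
- **Covariates:** keep the alcohol-infusion endpoints, but enter each session's own value instead of the V2–V5 difference. The difference needs both sessions, so it would exclude participants without V5 even from a mixed model. Also report the model without these covariates, because the alcohol taken at V5 may itself be affected by treatment.
- **Contrast:** for each active arm versus placebo, the change from the pre-experiment rating at V5 relative to the same change at V2, with 95% CI. Slopes between neighbouring time points are contrasts from the same model.
- **Section 5.1:** add a sentence that these scales are analysed from all available ratings under missing at random.

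The cost is SAP wording and slightly more code; both named packages fit such models. Missing at random must be stated as an assumption. The model cannot create V5 information for participants who did not attend, and it does not protect against missingness that depends on unobserved ratings.

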1 STUDY BACKGROUND

1.1 STUDY OBJECTIVES

The main research question is whether the current "Behavioral Test for the Development of medications for Alcohol Dependence" (TEMA) can demonstrate that the administration of acamprosate or ionized Calcium (Ca^{2+} = finished drug Calcium-Verla®) reduces the willingness to work for alcohol in a laboratory experiment following a 15- to 20-day period of alcohol abstinence.

The willingness to work for alcohol is determined by the cumulative number of work trials in the "constant attention task" (CAT). The change in this willingness due to the administration of acamprosate, Ca²⁺, or placebo is expressed as the difference in the cumulative number of work trials in the CAT per test day between Visit 2 (without medication) and Visit 5 (after administration of scamprosate, Ca²⁺ or placebo).

The hypothesis to be tested is that the administration of acamprosate compared to placebo or the administration of calcium ions compared to placebo, leads to a significant reduction in the willingness to work in the laboratory experiment to obtain alcohol.

Based on literature reports that form the basis of the sample size calculation, a relevant change is considered to be a reduction in blood alcohol concentration (BAC) of at least 0.1 per mille in one of the active treatment groups between Visit 2 and Visit 5 compared to the placebo group. In terms of the primary endpoint, this corresponds to a reduction in the cumulative number of work trials for alcohol infusions by 60.

Secondary objectives

The study aims to investigate whether:

- 1. the administration of acamprosate or calcium ions (Ca^{2+} = ready-to-use drug Calcium-Verla®) compared to placebo leads to altered subjective perception of alcohol effects
- 2. the efficacy of acamprosate or calcium ions can be predicted by basal levels or the change over time in measures of body calcium reserves reflecting a possible calcium deficiency
- 3. the administration of acamprosate or calcium ions reduces alcohol craving in daily life
- 4. the frequency of reported alcohol consumption during the imposed abstinence period differs between the treatment groups and how this affects the willingness to work for alcohol after the imposed abstinence period
- 5. participation in the study promotes the motivation to change drinking habits or alters drinking habits or the utilization of addiction treatment services

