4.2 PRIMARY ENDPOINT

The primary outcome measure is the difference in the cumulative number of work trials for alcohol in the "constant attention task" (CAT) [CATALC] between the first (V2) and second (V5) self-administration experiment, compared between the acamprosate vs. placebo and calcium vs. placebo treated groups [MED].

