6.3 EXPOSURE TO THERAPY AND COMPLIANCE

Randomization will be stratified according to the two criteria:

- a) Severity of addiction characteristics up to the time of V4
 - "High" if there is at least a moderate alcohol use disorder according to DSM-5, i.e., the presence of at least 4 of the 11 criteria, or if significant physical alcohol withdrawal symptoms were reported anamnestically or observed by study physicians (CIWA at V3 or V4 > 6 points).
 - "Low" if there is only a mild alcohol use disorder according to DSM-5, i.e., the presence of no more than 3 of the 11 criteria, and physical withdrawal symptoms were neither reported anamnestically nor observed by physicians..

b) Answer to the question at time V4 as to whether patients want to reduce their alcohol consumption ("yes" or "no")

This stratification aims to ensure that the distribution of these two characteristics does not differ between the three treatment arms before the start of treatment.

It is hypothesized that acamprosate will have a more pronounced effect the more severe the addiction-related pathological changes in the reward system are. This aspect is captured by the composite factor "Severity of Addiction Characteristics" (criterion a).

Since the overwhelming majority of acamprosate studies in humans only included patients who wanted to reduce or stop their alcohol consumption, the clinical efficacy insights of acamprosate are limited to this group. On the other hand, it seems

inappropriate to make the desire for reduction a prerequisite for participation, as based on animal experiments and the observations of Mason et al. (2006), acamprosate reduces alcohol consumption even when there is no explicit desire for change, especially under the specific conditions of prior enforced abstinence.

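### The only modelled arm comparison of subjective alcohol effects adjusts for post-randomisation infusion endpoints, so it does not estimate the total randomised effect and is an equal-exposure effect only under unstated assumptions

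*SAP*

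**What the plan says.** Section 6.5.1, question 1, asks: "does the administration of acamprosate or calcium ions compared to placebo lead to altered subjective perception of alcohol effects". Ratings on visual analogue scales (VAS) are taken at V2 and V5 "in order to compare their alcohol-induced changes between the 3 treatment arms". The model is then given: "Repeated measures ANOVA will be used for analysis, with primary and secondary endpoints of alcohol infusion as covariates". Correlation analyses between infusion endpoints and ratings follow, but these do not compare arms.

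The covariates are defined elsewhere in the SAP:

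- Section 4.2: "The primary outcome measure is the difference in the cumulative number of work trials for alcohol", taken between the two self-administration sessions. Section 1.1 describes it as "the difference in the cumulative number of work trials in the CAT per test day between Visit 2 (without medication) and Visit 5", the latter after study drug.
- Section 6.5.1, item b, gives a secondary example: "Difference in maximum and mean blood alcohol concentration (BAC) achieved during alcohol self-administration between visits 2 and 5". Break points and work for saline are also V2-to-V5 differences.

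The SAP does not say which secondary endpoints enter the model. Nor does it say whether the arm effect sought is the total effect or the effect at a given alcohol exposure.

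Section 6.5.1 also says that all these parameters are first described, that they are modelled only if something notable appears, and that the aim is to generate hypotheses.

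**The concern.** Randomisation protects an arm comparison when the adjustment variables are fixed before treatment. Here they are not. One stratification factor is the "Answer to the question at time V4 as to whether patients want to reduce their alcohol consumption" (section 6.3), so randomisation is not before V4 and V5 comes after it. Section 1.1 also states the change hoped for in the covariate. It takes a 0.1 per mille fall in BAC as relevant and adds that "this corresponds to a reduction in the cumulative number of work trials for alcohol infusions by 60".

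The model therefore holds constant an outcome that the drug is meant to move. Three things follow:

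- Any effect of the drug on ratings that acts through the amount of alcohol self-infused is removed.
- What is left can be distorted if work and ratings share a cause that was not measured.
- For a rating such as desire for more alcohol, work may be a consequence of the rating. Adjusting for it then removes part of a real effect.

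At stake is the only planned model for secondary objective 1, and the hypotheses that later studies would take from it.

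**Working it through.** The SAP gives no figure for this analysis and no SD, correlation or group size that bears on it, so there is nothing to reproduce. The check is algebraic, with assumed values in SD units.

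**Inputs.** A is the arm (0 placebo, 1 active). M is the V5-minus-V2 change in work for alcohol (or BAC). Y is the change in a VAS rating. Assumed: a, effect of drug on M; b, effect of M on Y; c, direct effect of drug on Y; r, correlation of the residuals of M and Y. Residual SDs are 1. I take the covariate to enter the equation for the rating change, that is, with a covariate-by-visit term; the SAP does not specify this.

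**Model.** M = a·A + e_m and Y = c·A + b·M + e_y, with corr(e_m, e_y) = r.

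- Unadjusted arm difference (total effect): c + a·b.
- Given A and M, the expected value of e_y is r·(M - a·A). So Y = (c - a·r)·A + (b + r)·M + error, and the adjusted arm effect is c - a·r.

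**Creating an effect** (c = 0, b = 0, truth 0):

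- a = -0.3, r = 0.3: 0 + 0.3 × 0.3 = +0.09.
- a = -0.5, r = 0.5: 0 + 0.5 × 0.5 = +0.25.
- a = -0.8, r = 0.5: 0 + 0.8 × 0.5 = +0.40.

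**Hiding an effect** (c = -0.30, b = 0, truth -0.30):

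- a = -0.5, r = 0.3: -0.30 + 0.15 = -0.15.
- a = -0.5, r = 0.5: -0.30 + 0.25 = -0.05.
- a = -0.8, r = 0.5: -0.30 + 0.40 = +0.10.

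**Effect only through less alcohol** (c = 0, a = -0.5, b = 0.5). The total effect is -0.5 × 0.5 = -0.25. Adjusted, it is 0.00 at r = 0 and +0.25 at r = 0.5.

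**Rating drives work.** Let Y = d·A + e and M = g·Y + e', with unit variances. The adjusted arm effect is d/(1 + g²). With d = -0.50 it is -0.50/1.25 = -0.40 for g = 0.5, -0.50/2 = -0.25 for g = 1, and -0.50/5 = -0.10 for g = 2.

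Simulation with 200,000 per arm agreed with both formulas to within about 0.01 SD.

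**Limit.** If r = 0 and the rating does not drive work, the adjusted effect equals c, the direct effect, without bias.

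**Illustrative rejection rates.** With no drug effect on ratings and b = 0, a nominal two-sided 5% test (|t| > 2.0), 4,000 replicates, assumed 20 to 50 per arm, a = -0.5 or -0.8 and r = 0.3 to 0.7, the adjusted model rejects in 8.0% to 94.5% of runs. The unadjusted comparison rejects in 4.3% to 5.7%.

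**Timing.** Section 4.3.1 schedules one rating ahead of the session, two within it and one afterwards. A whole-session change score therefore includes work done after three of the four ratings. For the first rating at V5, no alcohol has yet been infused in that session.

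**The case against.** The strongest case for the plan is that participants choose their own dose. An unadjusted contrast mixes altered perception of alcohol with having received less of it. In the example above, a drug with no direct effect on perception yields -0.25 SD unadjusted, which a reader could mistake for altered perception. Perception at equal exposure is a legitimate reading of objective 1 and may be why the infusion endpoints were chosen. This stands: adjustment is not wrong in itself, and neither contrast suffices alone. It does not rescue the planned covariates, because the SAP states neither that aim nor its assumptions, and whole-session change scores serve it poorly.

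A stable trait, such as individual sensitivity to alcohol reward, is a tempting source of bias. If it acts additively, it cancels from the change in work and from the arm-by-visit contrast in ratings. That also stands. What remains is causes specific to the visit, interaction with treatment, and ratings that drive work. The values of r used above are not established for change scores.

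A reader might infer that no unadjusted look at the arms is planned. The SAP does not support that: section 6.5.1 puts description first, and only an unadjusted model is missing. A reader might also take the rejection rates as this trial's error rates. They are not. The SAP sets no 5% test here (its 0.025 is for the two confirmatory hypotheses), the runs ignore the descriptive step, and they let infused alcohol have no effect on ratings, which is implausible for a rating such as feeling drunk. The adjusted coefficient c - a·r does not depend on b, so that last point limits the claim about the total effect, not the one about the direct effect.

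**Conclusion.** The point holds in limited form. The single modelled arm comparison for secondary objective 1 conditions on outcomes measured on randomised drug. It does not estimate the total randomised effect, and it estimates an equal-exposure effect only if there is no shared visit-specific cause and no path from perception to work. Under the assumed values the distortion runs from nothing (r = 0, no reverse path) to 0.40 SD, in either direction of interpretation: an effect created, or one hidden. Its actual size in this trial cannot be derived from the SAP.

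It would be going too far to conclude that the trial's main result is compromised. The analysis is exploratory, conditional on the descriptive step and separate from the confirmatory tests. The change is worth making because it is cheap and because hypotheses for later work would rest on this model.

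**What to change.** In section 6.5.1, question 1, specify two analyses for each VAS measure.

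1. **Randomised comparison.** V5 ratings by arm, with two contrasts against placebo, adjusted for the V2 value of the same measure and the two stratification factors (addiction severity; wish to reduce drinking). Include no post-randomisation covariate. State that this is the total effect, including what acts through the amount self-infused.
2. **Supportive comparison at equal exposure.** One model using BAC, or cumulative infusions, up to each rating time in place of whole-session V2-to-V5 differences. Label it non-randomised, and state that it assumes no unmeasured visit-specific common cause and no effect of the rating on work.

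The cost is SAP wording and one extra model. No new data are needed if BAC or infusion counts are available at the rating times; section 4.3.1 already has cumulative work logged every 30 seconds. The downside is that the first contrast alone cannot separate altered perception from lower intake, so both must be shown together.
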